15.3. ADDITIONAL EFFICACY

15.3.1. Additional Efficacy Variables & Derivations

15.3.1.1.

Change from baseline in trough clinic seDBP, seSBP, and MAP at all visits of the DB Phase, excluding the Week 6/Final Visit (Week 2 and Week 4) for AZM and losartan.

15.3.1.2.

Change from baseline in trough clinic seDBP, seSBP, and MAP at all visits of the OL Phase, including Week 52/Final Visit.

15.3.1.3.

Percentage of subjects who achieve the following additional BP targets (for seSBP, seDBP, both):

All Subjects:

<90th percentile at Week 6 and Week 52/Final Visit of the DB Phase and OL Phase.

Subjects with chronic kidney disease (CKD):

- <90th percentile at Weeks 6, 8, and 52/Final Visits of the DB Phase, Withdrawal Phase, and OL Phase.
- <50th percentile at Weeks 6, 8, and 52/Final Visits of the DB Phase, Withdrawal Phase, and OL Phase.

15.3.1.4.

15.3.2. MISSING DATA METHODS FOR ADDITIONAL EFFICACY VARIABLE(S)

15.3.2.1.

For Change from baseline in trough clinic seDBP, seSBP, and MAP at Week 2 and Week 4 of the DB Phase, last observation carried forward (LOCF) method for missing data will be used for the sensitivity analysis.

15.3.2.2.

Observed change from baseline in trough clinic seDBP, seSBP, and MAP at all visits of the OL Phase will be

Document: 2014-000674-18 Statistical Analysis Plan Version 7.0 Version Number: 7.0

Author: Version Date: 13JAN2020

Template No.: CS_TP_BS016 Revision 5 Reference: CS_WI_BS005

Effective Date: 01Apr2018

used, including Week 52/Final Visit, no method will be used for missing data.

15.3.2.3.

For the analysis of subjects who achieve the BP targets at Week 6/Final Visit of DB phase and Week 8/Final Visit of Withdrawal phase (for seSBP, seDBP, both), LOCF will be used. Sensitivity analyses on trough seDBP, seSBP, and MAP will be performed on observed values and using multiple imputation for missing trough BP data. No missing data will be used for percentage of subjects who achieve the BP targets at Week 52.

15.3.3. Analysis of Additional Efficacy Variables

15.3.3.1.

Change from baseline in trough clinic seDBP, seSBP, and MAP at visits Week 2 and Week 4 of DB Phase will be will be analyzed using the same MMRM model that is described in section 15.2.3.2 and the result will come from the same model as well.

15.3.3.2.

No statistical model will be used for Change from Baseline in trough clinic seDBP, seSBP, and MAP at all visits of the OL Phase, including Week 52/Final Visit. Only descriptive statistics will be provided

15.3.3.3.

The analysis for whether a subject who achieves the BP targets at Week 6/Final Visit in the DB Phase (for seSBP, seDBP, both), will be logistic models on observed data with treatment (AZM low, med, high dose and losartan), age (Tanner stage <3, ≥3), race (Black or African American, Non- Black or African American) and weight (<50 kg, ≥50 kg) as fixed effects and baseline clinic seated BP as a covariate. The number and percentage of subjects who achieved target BP will be presented, along with the odds ratios and associated 95% CIs. Sensitivity analyses on trough seDBP, seSBP, and both will be performed for DB analysis on observed values and using multiple imputation for missing trough BP data to assess the impact of LOCF methodology and drop-outs. For Week 52/Final Visit of the OL Phase, the number and percentage of subjects who achieve the BP targets will be provided.

For subjects with CKD, the analysis for weather a subject who achieves the BP targets at week 6/Final Visit in the DB phase and week 8/Final visit in the WD phase (for seSBP, seDBP, both), will be logistic models on observed data with treatment (AZM low, med, high dose and losartan), age (Tanner stage <3, ≥3), race (Black or African American, Non- Black or African American) and weight (<50 kg, ≥50 kg) as fixed effects and baseline clinic seated BP as a covariate. The number and percentage of subjects who achieved target BP will be presented, along with the odds ratios and associated 95% Cls. . Sensitivity analyses on trough seDBP, seSBP, and both will be performed for DB analysis on observed values and using multiple imputation for missing trough BP data to assess the impact of LOCF methodology and drop-outs. For Week 52/Final Visit of the OL Phase, the number and percentage of subjects with CKD who achieve the BP targets will be provided.

7.0 Document: 2014-000674-18 Statistical Analysis Plan Version 7.0 Version Number: Author: Version Date: 13JAN2020

Template No.: CS_TP_BS016 Revision 5 Reference: CS_WI_BS005

Effective Date: 01Apr2018

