6.1.1 Subjects

Children, both male and female, between 6 to <18 years of age at baseline with a historical or new diagnosis of primary or secondary hypertension who are a minimum weight of 25 kg will be evaluated for eligibility during Screening/Visit 1. Hypertension is defined as clinic seDBP ≥ 95 th percentile for age, gender, and height or ≥ 90 th percentile by age, gender, height if chronic renal disease, diabetes, heart failure or hypertensive target organ damage is present according to percentiles published in the US National Heart Lung and Blood Institute (NHLBI) Fourth Report on the Diagnosis, Evaluation, and Treatment of High Blood Pressure in Children and Adolescents

[5]. As described in [Section 9.1.5](#), BP will be measured 3 times at each visit, and the average of these serial measurements will serve as the BP value of the actual visit and be used for determination of subject eligibility.

Subjects can either be untreated or currently receiving no more than 2 antihypertensive drugs, are willing to discontinue their current therapy, and in the opinion of their treating physician, could safely discontinue current therapy. Prior to this amendment, the approximate expected percentage of subjects with secondary hypertension is between 40%-60% and no more than \approx 25% of subjects will be post-renal transplant patients and no more than \approx 60% of subjects will weigh greater than or equal to 50 kg at Baseline. Due to recruitment difficulties, the expected number of secondary hypertensive subjects and subjects weighing less than 50 kg was not achieved. The revised expected percentage of subjects with secondary hypertension and subjects weighing less than 50 kg will be at least 20% of the total subject population.

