A logistic model with treatment, age and weight as fixed effects and baseline clinic BP as covariate will be used to analyze the percent of subjects achieving target BP at Week 8/Final Visit of the Withdrawal Phase. The odds ratio and associated 95% confidence interval (CI) will be estimated. Similar logistic regression may be performed on percent of subjects achieving target BP at Week 6/Final Visit of the DB Phase. The target blood pressures (percentiles by age, gender and height) evaluated as secondary or additional endpoints include the following (at Week 6/Final Visit of the DB Phase and at Week 8/Final Visit of the Withdrawal Phase):

- seDBP <90th percentile.
- seSBP <90th percentile.
- Both seDBP<90th percentile and seSBP< 90th percentile.

Additional BP target endpoints to be tabulated (for seDBP, seSBP, and both) include:

- <90th percentile at Week 6/Final Visit of the DB Phase and Week 8/Final Visit of the Withdrawal Phase, for subjects with CKD.
- <50th percentile at Week 6/Final Visit of the DB Phase and Week 8/Final Visit of the Withdrawal Phase, for subjects with CKD.
- <90th percentile at Final Visit of OL Phase, for all subjects.
- <90th percentile at Final Visit of OL Phase, for subjects with CKD.
- <50th percentile at Final Visit of OL Phase, for subjects with CKD.

Descriptive statistics will be provided for the change from Baseline as well as the difference between each AZM treatment and losartan for 24-hour, 12-hour, daytime, night time, and trough ABPM SBP/DBP. Additional analysis of the SBP/DBP by ABPM will be performed where appropriate.

The efficacy analysis on DB Phase will be based on last-observation-carried-forward (LOCF) data set, unless otherwise specified. In the LOCF analysis data set, the last postbaseline double-blind observed value will be carried forward and used for all subsequent scheduled time points in the DB

Phase where data are missing (eg, the subject has missing data or has dropped out of the study). The efficacy analysis for the target BP will also be based on the LOCF data set. Sensitivity analyses on trough seDBP, seSBP, and MAP will be performed on observed values and using multiple imputation for missing trough BP data to assess the impact of LOCF methodology and drop-outs.

Subgroup analyses such as gender, race, region, diagnosis (primary versus secondary hypertension), and other important baseline factors may be performed on the primary endpoint and secondary endpoints as appropriate.

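### SAP 15.3.3.3 adds an eight-parameter logistic model for CKD subjects with no sparse-data rule; at plausible subset sizes some treatment odds ratios are likely to have no finite estimate, especially at Week 8

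*SAP*

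**What the plan says.** Protocol 13.1.3 specifies a logistic model for the <90th percentile targets, with treatment, age, weight and baseline BP. The CKD targets come under a different lead-in, "Additional BP target endpoints to be tabulated (for seDBP, seSBP, and both) include", and that list includes "<50th percentile at Week 6/Final Visit of the DB Phase and Week 8/Final Visit of the Withdrawal Phase, for subjects with CKD".

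SAP 15.3.1.3 carries both CKD targets, among them "<50th percentile at Weeks 6, 8, and 52/Final Visits of the DB Phase, Withdrawal Phase, and OL Phase". SAP 15.3.3.3 then specifies: "For subjects with CKD, the analysis for weather a subject who achieves the BP targets" at Week 6, and likewise at Week 8, "will be logistic models on observed data with treatment (AZM low, med, high dose and losartan), age (Tanner stage <3, ≥3), race" and weight group "as fixed effects and baseline clinic seated BP as a covariate". Counts and percentages are still to be presented, now with odds ratios and 95% confidence intervals.

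The SAP sets no minimum subset size or event count for this model and names no exact or penalised alternative. Its one non-convergence rule (15.2.3.2) concerns the covariance structure of the MMRM. SAP 3.6, the section for changes from the protocol, points only to the sample size section.

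Neither document states how many CKD subjects are expected. The nearest figure is in Protocol 6.1.1: "The revised expected percentage of subjects with secondary hypertension and subjects weighing less than 50 kg will be at least 20" per cent of the total.

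**The concern.** A logistic model has no finite maximum-likelihood estimate for a treatment odds ratio when one of the two groups compared has no responders. Adjusting for further binary factors in a small sample makes such separation more likely. Software then reports the value at which the iterations stopped, with an interval that means little. The CKD subset may be small, and the <50th percentile target is hard to reach from a hypertensive baseline.

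Read literally, the SAP text covers two targets, three BP definitions (seSBP, seDBP, both) and two visits: 2 × 3 × 2 = 12 models. Several could put uninterpretable odds ratios into the study report, and the plan does not tell the programmer what to do when that happens.

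**Working it through.** The plan gives no figure for this analysis, so there is none to reproduce. CKD numbers, response rates and covariate shares below are assumptions.

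**1. Parameters (SAP 15.3.3.3).** Intercept 1 + treatment 3 + Tanner 1 + race 1 + weight 1 + baseline BP 1 = 8.

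**2. Subset size.** The total is at least 213 and the secondary-hypertension floor is 20%: 0.20 × 213 ≈ 43. Taking half to all of these as CKD gives 21 to 43.
- Week 6, four arms at 1:1:1:1: 21/4 ≈ 5 to 43/4 ≈ 11 per arm.
- Week 8, AZM-treated children only: 3/4 × 21 ≈ 16 to 3/4 × 43 ≈ 32. Half go to placebo (8 to 16), leaving 8/3 ≈ 2.7 to 16/3 ≈ 5.3 per dose.

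**3. Response rate for seDBP <50th percentile.** Protocol 6.2.5 equates 4-5 mm Hg with the step from the 95th to the 90th percentile. Under normality that step is 1.645 − 1.282 = 0.363 SD, so one SD is about 11.0 to 13.8 mm Hg. The 90th to the 50th percentile is then 1.282 × 11.0 ≈ 14 to 1.282 × 13.8 ≈ 18 mm Hg. Assume a mean fall of 6-12 mm Hg, an SD of 8.3-10.5 and a required fall of 14-20 mm Hg. The extremes are 1 − Φ((20 − 6)/8.3) ≈ 5% and 1 − Φ((14 − 12)/10.5) ≈ 42%. Rates of 10-20% are plausible, and so are higher ones.

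**4. Check without covariates: chance that at least one group has no responders** (common rate p).
- Week 6, n subjects: 1 − [1 − (1−p)^(n/4)]^4.
- Week 8, m AZM-treated, doses L, M and H against placebo: 1 − [1 − (1−p)^(m/6)]^3 × [1 − (1−p)^(m/2)].

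| | p = 10% | p = 20% |
|---|---|---|
| Week 6, n = 21 / 32 / 43 | 97 / 89 / 79% | 77 / 52 / 32% |
| Week 8, m = 16 / 24 / 32 | 99 / 97 / 93% | 93 / 81 / 67% |

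For example, at n = 43 and p = 20%: 0.8^10.75 = 0.091, and 1 − 0.909^4 = 32%.

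At p = 30%, Week 6 with n = 43: 0.7^10.75 = 0.022, and 1 − 0.978^4 ≈ 8%. Week 8 with m = 32: 1 − (1 − 0.149)^3 × (1 − 0.003) ≈ 39%.

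**5. Full eight-parameter model.** Data were simulated with no true effects, Tanner <3 in 25%, Black 20% and <50 kg 40%, and each data set was tested for separation. Share with at least one non-finite treatment odds ratio:
- Week 6, n = 21 / 32 / 43: 99 / 92 / 82% at p = 10%, and 87 / 51 / 34% at p = 20%.
- Week 8, m = 16 / 24 / 32: 96 / 84 / 67% at p = 20%. At p = 10% step 4 already gives 93% or more.

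**6. Sensitivity.** A second simulation used slightly different covariate shares, a baseline BP slope and small drug effects above a reference rate p, which raise the response. For 43 CKD subjects at Week 6 it gave 66% at p = 10%, 22% at 20% and 4% at 30%. For a total of 43 at Week 8 against placebo it gave 87%, 51% and 27%. The level falls, but Week 8 remains the worse visit.

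The Week 8 figures use placebo as the reference. The SAP's CKD sentence lists losartan and omits placebo. That is a separate error, and correcting it does not remove the sparse-data problem.

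**The case against.** Several stronger readings are tempting, and the documents do not support them.

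- *The SAP replaces the protocol's tabulation.* It does not. Counts and percentages stay, and the model is added to them. Protocol 13.1 leaves methodological detail to the SAP, so the addition is permissible. What is missing is its entry in SAP 3.6.
- *The model cannot be estimated, or its odds ratios will usually be non-finite.* This is too broad. At Week 6 with about 43 subjects and 20% at target, most fits give finite treatment odds ratios. With 60 subjects step 4 gives 1 − (1 − 0.8^15)^4 ≈ 13%. The <90th percentile target, which the same text covers, may well have a response of 30% or more. Counting separation in any term also overstates the harm: in the second simulation (Week 6, 43 subjects, 20%) any parameter was non-finite in 40% of data sets, at least one treatment odds ratio in 22%, and all three in 9%.
- *The CKD subset is known to be small.* It is not. The 20% is a floor for secondary hypertension, not for CKD, and Protocol 6.2.1 expects many CKD subjects without giving a number.
- *Ordinary maximum likelihood is specified.* The SAP says only that logistic models will be used. A penalised fit is neither named nor excluded.

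These are additional endpoints outside the testing sequence. All of this limits the size of the point. It does not supply the missing sparse-data rule or the missing record of the change.

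**Conclusion.** The concern holds in a limited form. SAP 15.3.3.3 adds an eight-parameter model to a subset analysis that the protocol only tabulates, with no sparse-data fallback and no entry in SAP 3.6.

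Assuming 21-43 CKD subjects and 10-20% at target, at least one treatment odds ratio has no finite maximum-likelihood estimate in about 34-99% of trials at Week 6. At Week 8, with 16-32 AZM-treated children and placebo as reference, the share is about 67-100%. With small drug effects the lower ends fall to 22% and 51%. At Week 6 the risk is small with about 43 or more subjects and a response of 30% or more.

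All of these figures depend on a CKD count and a response rate that the documents do not give. The primary result is unaffected, and the point is minor.

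**What to change.** In SAP 15.3.3.3, keep the planned counts and percentages for CKD subjects, add exact 95% confidence intervals by arm and for pooled AZM, and delete the eight-parameter CKD model.

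If a comparison is wanted, prespecify one pooled AZM contrast per visit: against losartan at Week 6 and against placebo at Week 8. Fit it by Firth-penalised or exact logistic regression, adjusted for baseline BP only. List the change in SAP 3.6.

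The cost is SAP wording and somewhat less programming. What is lost is the set of dose-level adjusted odds ratios in CKD subjects.

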15.4. EXPLORATORY EFFICACY

15.4.1. EXPLORATORY EFFICACY VARIABLES & DERIVATIONS

15.4.1.1.

Change from baseline to Week 6/Final Visit of the DB Phase and to Week 52/Final Visit of the OL Phase in 24hour, 12-hour, daytime, night time, and trough DBP and SBP by ABPM.

15.4.1.2.

AZM dose response for change from Baseline to Week 6/Final Visit of the DB Phase, Week 2 and Week 4 of the DB Phase in clinic seDBP, seSBP and MAP.

15.4.1.3.

Primary endpoint and secondary endpoints for subgroup analysis.

15.4.2. MISSING DATA METHODS FOR EXPLORATORY EFFICACY VARIABLE(S)

15.4.2.1.

For ABPM results, no missing data method will be used.

15.4.2.2.

For analysis of AZM dose response of the DB phase, LOCF will be used for missing data.

15.4.2.3.

Same method for missing data will be used for subgroup analysis of primary and secondary endpoints as that in Section 15.1.2 and 15.2.2.

15.4.3. Analysis of Exploratory Efficacy Variables

15.4.3.1.

For Change from Baseline to Week 6/Final Visit of the DB Phase in 24-hour, 12-hour, daytime, night time, and trough DBP and SBP by ABPM, descriptive statistics will be provided for the change from Baseline as well as the difference between each AZM treatment and losartan for 24-hour, 12-hour, daytime, night time, and trough ABPM SBP/DBP. For Change from Baseline to Week 52/Final Visit of the OL Phase in 24-hour, 12hour, daytime, night time, and trough DBP and SBP by ABPM, descriptive statistics will be provided for the change from Baseline for 24-hour, 12-hour, daytime, night time, and trough ABPM SBP/DBP.

2014-000674-18 Statistical Analysis Plan Version 7.0 Version Number: 7.0 Document: Author: Version Date: 13JAN2020

Template No.: CS_TP_BS016 Revision 5 Reference: CS_WI_BS005

Effective Date: 01Apr2018

Daytime is defined as 6 am – 9:59 pm Nighttime is defined as 10 pm - 5:59 am

Profile plots (line with symbol at each visit with +/- 1 SE error bars) will be displayed for the observed seDBP and seSBP and the change in seDBP and seSBP from baseline to Week 6 and to Week 52 in 24-hour, 12-hour, daytime, night time by ABPM.

15.4.3.2.

Exploratory dose response analysis using only AZM low, med and high dose groups, for change from Baseline to Week 6/ Final Visit, Week 2, Week 4 of the DB Phase in clinic seDBP, seSBP and MAP will be performed using linear regression model with weight adjusted dose (mg/kg) as the continuous covariate. LOCF will be used for missing data. The intercept with Standard Error and estimate of the coefficient with Standard Error will be displayed with the summaries. Additionally, an ANCOVA with treatment, age and weight as fixed effects, and baseline seDBP, seSBP or MAP as covariate will be performed to assess between-group comparisons.

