Changes in various parameters of DBP and SBP by ABPM will be evaluated as exploratory endpoints in this study. The utility of ABPM in adult hypertension is well established as both a diagnostic and prognostic tool [34-38]. In addition, ABPM is gaining acceptance in clinical practice as a useful diagnostic tool in children and adolescents [39,40]. For example, ambulatory BP readings may be useful in evaluating or confirming that BP control is maintained throughout the day in children with target organ damage, or to differentiate between primary and secondary forms of hypertension, which may exhibit different diurnal profiles [40,41]. Advantages of ABPM in the clinical trial setting include the ability to evaluate BP changes throughout the dosing interval and a reduced susceptibility to observer bias and placebo effect.

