9.1.15 Ambulatory Blood Pressure Monitoring

ABPM is a noninvasive technology to measure ambulatory BP during at least 24 hours. The device is programmed by the investigator or designee to measure BP and heart rate at set intervals during the day and night. The subject wears a compact and lightweight (about 1 pound/500 g or less) device that does not interfere with daily activities. Measurements are stored in the device and later uploaded onto a computer.

An Arbor-selected vendor will provide oscillometric ABPM units. The proper cuff size will be selected according to the circumference of the non-dominant arm. ABPM will be performed while subjects participate in their regular daily activities; however, each subject will be advised against participating in excessively vigorous physical activities or contact sports during the ABPM procedure. Recording will begin immediately after dosing. The reading frequency will be programmed for pre-set intervals that are more frequent during the daytime. When interference or error in the reading occurs, the process will be automatically repeated.

All subjects will have the opportunity to participate in serial 24-hour ABPM recordings. The baseline ABPM will be performed on Day -1/Visit 3 after subject eligibility has been verified but before randomization. Subjects who have a baseline ABPM procedure that meets predefined quality criteria will undergo a second recording for the 24 hours preceding the Week 6 visit (ie, Week 6 -1 Day/Visit 7). An optional ABPM may also be conducted one day prior to the last day of the OL Phase (ie Week 52 -1 Day/Visit 15) for subjects with a baseline ABPM that meets quality criteria. Subjects who do not wish to participate in the ABPM procedure but otherwise qualify for the study will be allowed to enroll.

Subjects should be instructed to withhold their dose of study medication on the morning when an ABPM recording is scheduled to begin, and that day's dose of study medication will be administered in the clinic. The ABPM measurement should begin immediately after dosing, and every effort should be made to initiate all ABPM recordings at the same time of day. Subjects will

CONFIDENTIAL

be instructed to return to the clinic on the following day approximately 24 hours after the device is fitted so that the quality of the ABPM measurement can be verified and the device can be removed. If the ABPM does not meet quality criteria but study entry criteria are met, the subject may be enrolled.

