- (h) Includes sitting and standing BP and pulse. Obtain a second set of 3 seated measurements if any of the initial BP readings differ by >8 mm Hg for SBP or >5 mm Hg for DBP; if clinic BP at any visit exceeds the 99th percentile for age, gender, and height by 15 mm Hg for SBP or 10 mm Hg for DBP, a repeat measurement should be obtained within 48 hrs and the subject withdrawn if BP remains elevated.
- (i) In the OL Phase, if BP is above the target (ie, seDBP and/or seSBP are not <90 th percentile for age, gender, and height), titrate study medication or add additional medication according to the recommended treatment algorithm provided in [Figure 6.b](#). A lower BP target may be employed for subjects with CKD at the investigator's discretion.
- (j) Previous medical history documentation is acceptable if assessment was performed within the previous 6 months.
- (k) Spontaneous reports of PTEs should be collected from the time that informed consent is acquired until the first dose of study drug.
- (l) Spontaneous reports of AEs and SAEs should be collected from the time of the first dose of study drug through 14 and 30 days, respectively, after the last dose.
- (m) Includes the following listed in [Table 9.a](#)- hematology, urinalysis and all serum chemistry except for HgA1c; fasting is not required.
- (n) Renal subpanel only; the renal subpanel may also be requested by the investigator at unscheduled visits after study drug is titrated.
- (o) For diabetic subjects only
- (p) One PK sample will be obtained 1 to 2 hrs post-dose on D1/V4. At W4/V6, 1 sample will be collected at trough (ie, 24 to 36 hours after the previous dose) and 1 at 3 to 5 hrs post-dose. At W6/V8, a sample will be obtained at trough.
- (q) Only female subjects \geq 12 years old and younger girls deemed by the investigator to be of reproductive potential.
- (r) Includes serum and urine pregnancy test at Screening and urine pregnancy test at all other visits.
- (s) Required only for subjects \geq 12 years old; may be performed for younger children if deemed appropriate by the investigator. Results must be negative for the subject to continue in the study.
- (t) The Week 6 ABPM should be completed only for subjects with a baseline ABPM that met quality criteria. The Week 52 ABPM is optional for subjects with a baseline ABPM that met quality criteria; participating subjects should return to the clinic \approx 24 hours after the fitting for device removal.

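### Week 6 ABPM differences between AZM and losartan are planned as unadjusted change-score differences; an ANCOVA on the baseline recording would be modestly more precise

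*SAP*

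**What the plan says.** The ABPM endpoints are exploratory. Protocol 6.2.5 states: "Changes in various parameters of DBP and SBP by ABPM will be evaluated as exploratory endpoints in this study". The variable in SAP 15.4.3.1 is a change score: "For Change from Baseline to Week 6/Final Visit of the DB Phase in 24-hour, 12-hour, daytime, night time, and trough DBP and SBP by ABPM". For it, "descriptive statistics will be provided for the change from Baseline as well as the difference between each AZM treatment and losartan". No model, covariate, test or confidence interval is named. SAP 7.1 lists baseline seDBP, seSBP and MAP among the covariates but no ABPM value, and the default summaries in SAP 6.6 stop at n, mean, SD, minimum, median and maximum.

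Participation is voluntary (Protocol 9.1.15): "Subjects who do not wish to participate in the ABPM procedure but otherwise qualify for the study will be allowed to enroll". A second recording depends on a usable first one: "Subjects who have a baseline ABPM procedure that meets predefined quality criteria will undergo a second recording". Footnote (t) to the schedule in Protocol 9.3 repeats this: "The Week 6 ABPM should be completed only for subjects with a baseline ABPM that met quality criteria".

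Two other places matter. SAP 15.4.3.2, also exploratory, compares the AZM groups on clinic blood pressure with an ANCOVA that has the matching baseline value as covariate. Protocol 13.1.3 leaves room for more: "Additional analysis of the SBP/DBP by ABPM will be performed where appropriate". The SAP does not say what that would be.

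**The concern.** Subtracting baseline fixes the baseline slope at 1. When the slope of Week 6 on baseline is below 1, the usual case for blood pressure, subtraction over-corrects. This has two consequences for the AZM versus losartan contrast:

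- It carries more sampling noise than a baseline-adjusted estimate from the same children.
- If one arm happens to start higher, regression towards the mean makes that arm look more effective.

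The covariate needed to deal with both is complete for every child in the analysis. As written, the reported differences also come without a stated measure of their own precision. At stake are the clarity and precision of the 24-hour evidence on the comparison with losartan, a secondary objective. No confirmatory claim is involved.

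**Working it through.** The documents give no ABPM sample size, SD, correlation or participation figure, so there is no plan figure to reproduce. Everything below rests on stated assumptions.

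**1. Precision.** Let baseline and Week 6 ABPM have common variance s² and correlation rho. Per child:

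- change score: Var = 2(1 − rho)s²
- ANCOVA residual: Var = (1 − rho²)s²
- ratio, ANCOVA to change score: (1 − rho²) / [2(1 − rho)] = (1 + rho)/2

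| Assumed rho | Variance ratio | SE ratio | Variance cut | SE cut | Equivalent extra children (1/ratio − 1) |
|---|---|---|---|---|---|
| 0.5 | 0.75 | 0.866 | 25% | 13% | 33% |
| 0.6 | 0.80 | 0.894 | 20% | 11% | 25% |
| 0.7 | 0.85 | 0.922 | 15% | 8% | 18% |
| 0.8 | 0.90 | 0.949 | 10% | 5% | 11% |

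Over a wider range, the variance ratio is 0.65 at rho = 0.3 and 0.95 at rho = 0.9, so the SE falls by about 19% and 3%.

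Equal variances set the size of the gain, not its sign. With unequal SDs s_x (baseline) and s_y (Week 6), the change-score variance exceeds the ANCOVA variance by (s_x − rho·s_y)², which is never negative.

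**2. Small arms.** Simulating two arms with baseline as the only covariate (8,000 replicates per setting) gave SE ratios of 0.88, 0.93 and 0.96 at 23 per arm, and 0.88, 0.95 and 0.97 at 12 per arm, for rho = 0.5, 0.7 and 0.8. The gain shrinks slightly but remains.

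**3. In mm Hg, one AZM dose versus losartan.** Take 52 per arm and 10% dropout from Protocol 13.3. Assume 50% or 25% ABPM participation: 52 × 0.9 × 0.5 = 23.4 per arm, or 52 × 0.9 × 0.25 = 11.7. Borrow 8.3 mm Hg as the SD of change. The protocol gives that figure for clinic seDBP from Week 6 to Week 8, so here it is only illustrative. The change-score half-width is t × 8.3 × √(2/n). For ANCOVA it is multiplied by √((1 + rho)/2), with one degree of freedom fewer and a small-sample correction.

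| n per arm | Change score | ANCOVA, rho 0.5 | rho 0.7 | rho 0.8 |
|---|---|---|---|---|
| 23.4 | 4.89 | 4.28 | 4.56 | 4.69 |
| 11.7 | 7.13 | 6.35 | 6.76 | 6.95 |

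The 95% half-width narrows by 0.2 to 0.6 mm Hg at 23.4 per arm, and by 0.2 to 0.8 at 11.7.

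**4. Chance imbalance.** If the arms differ at baseline by D, the expected change-score contrast, given D, is off by (1 − rho)D in favour of the higher-starting arm. Assume an ABPM SD of 8 mm Hg. A one-standard-error imbalance is 8 × √(2/23) = 2.4 mm Hg at 23 per arm and 8 × √(2/12) = 3.3 at 12. For rho from 0.8 to 0.5 the shift is then about 0.5 to 1.2 mm Hg, and 0.7 to 1.6 mm Hg. Averaged over randomisations D is zero, so this is not a bias of the method.

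**The case against.** The strongest reply is that nothing here is an error. The SAP follows Protocol 13.1.3 closely, the endpoint is optional and exploratory, and no test, alpha or sample size depends on it. A descriptive plan is legitimate, and the protocol permits further ABPM analysis. SAP section 10 tabulates baseline ABPM by arm with p-values, so an imbalance would be visible. The profile plots carry SE bars, and the table templates mentioned in SAP section 8, which were not available, might contain an interval. The ANCOVA would also add 5 measures × 2 pressures × 4 contrasts = 40 interval estimates.

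Most of this stands, and it sets the priority. It does not remove the point. The permission for further analysis commits to no method, and a model chosen after the unblinding described in SAP 4.2 would be post hoc. Section 10 covers all randomised children, not those with paired recordings, and showing an imbalance does not adjust for it. SE bars on profile plots are not an interval for the difference between arms. Exploratory status does not explain the omission either, because 15.4.3.2 is exploratory and adjusts for baseline.

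Three stronger readings are tempting, and the documents do not support them:

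- *Baseline ABPM is ignored.* It is not: each child's own baseline is subtracted. What is missing is an estimated slope.
- *Voluntary participation biases the comparison.* Opting in and the first recording precede allocation: "The baseline ABPM will be performed on Day -1/Visit 3 after subject eligibility has been verified but before randomization". This limits numbers and generalisability but does not of itself unbalance the arms. Loss of Week 6 recordings after randomisation is a separate matter.
- *The ABPM arms are small and materially imbalanced.* No participation figure is given, so this cannot be asserted.

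**Conclusion.** The point holds as a low-priority improvement in efficiency. SAP 15.4.3.1 plans unadjusted change-score differences although the matching baseline is always available. These differences are unbiased under randomisation. For an assumed correlation of 0.5 to 0.8 and equal variances, ANCOVA would cut their variance by 25% to 10% and their SE by about 13% to 5%; at 0.7 to 0.8 the SE gain is a modest 5% to 8%. ANCOVA would also remove the (1 − rho)D shift that a chance baseline difference produces. A reader might infer that the ABPM comparison is invalid or that the trial's conclusions are at risk, but neither follows: the primary analysis, its error control and the sample size are untouched. The size depends on a correlation that the documents do not give, and the mm Hg figures also rest on assumed participation and on a borrowed or assumed SD.

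**What to change.** Before unblinding, add to SAP 15.4.3.1 an ANCOVA of the Week 6 change for each ABPM measure, with treatment, Tanner stage, weight group and race as factors and the matching baseline ABPM value as covariate. Add the baseline ABPM values to the covariate list in SAP 7.1. Report LS mean differences for each AZM dose and for pooled AZM versus losartan, with 95% confidence intervals and the number of children contributing per arm. Label the results exploratory and state that there is no multiplicity control. Keep the descriptive table. If treatment codes have already been opened, the same analysis can still be run but should be labelled post hoc.

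The cost is a few sentences, reuse of the ANCOVA code already needed for clinic blood pressure, a few degrees of freedom (which matter slightly if arms are small), and additional exploratory output.
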